Medical Outcomes Study Short Form 36	X		
Internet Self-efficacy Scale	X	X	X
Clinical Trials Literacy	X	X	X

Message Effectiveness Scale		X	X
Clinical Vignette			X

IV. DATA ANALYSIS AND DATA MONITORING

Throughout the study, [name] will oversee data entry and verification, ensure adherence to coding, clean and edit protocols. Data will be maintained on a password-protected PC with backup copies kept on external disks in a secured location.

Participant-identifying information will be kept in a locked file cabinet with only numerical identifiers in computer files.

Hypothesis 1: Participants exposed to tailored messages about clinical trial literacy will exhibit greater likelihood in participating in clinical trials than those exposed to NYU's standard website. Secondly, we expect them to show greater likelihood to refer others to clinical trials as well.

Analysis: While the primary goal of the study is to develop and test effectiveness of tailored messages to overcome identified barriers to participating in clinical trials, the secondary goal is to examine factors likely to facilitate adoption of such messages. All participants in the intervention arm will have been exposed to all tailored web-based messages. To compare participants who exhibited improvement in health literacy and those who did not 2-months post-enrollment, t-tests and chi-squared tests will be used. Baseline subjective factors will be entered in a logistic regression model in order to determine which factors are associated with higher likelihood of (a) registering to participate in clinical trials, contrasting individuals in the two study arms and (b) referring others to participate as well. Multivariate analysis of covariance will be used to assess effects of messages on the secondary outcome: health literacy scores; effects of sociodemographic confounders will be adjusted.

Hypothesis 2: Greater likelihood of participating in clinical trials will be mediated by greater health literacy and/or self-efficacy independent of other individual-level factors (medical, knowledge, attitude/beliefs, and intrinsic motivation) and contextual-level factors (social support and socio-economic position).

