Analysis: We will examine the path toward greater participation in clinical trials using Structural Equation Modeling (SEM). SEM will determine influences of mediating/moderating factors on the role of tailored messages in improving participation rates in existing clinical trials. Specifically, we will use moderated path analysis from Baron and Kenny's model. We chose these factors based on research showing acceptable effect size in predicting likelihood of increased participation. Alternatively, we will employ probabilistic modeling methods (e.g., Bayesian Belief Network) to investigate interactions (omni-directionality) among predictors and different pathways to the desired study outcomes, determining which factors best differentiate cases and controls. Thus, we will ascertain patient characteristics most likely to show improvement in rates of participation.

V. STATISTICAL PLAN

Power Calculations: Primary Objective: Assuming a medium effect size ($d = 0.32$), as derived from Cohen, and a sample size of 100, the study will be adequately powered (> 80%) to detect significant differences between participants likely to show improvement in health literacy scores and those who are not using Fisher's Exact tests (critical $X^2 = 6.58$). This will also permit detection of a significant increase in the number of participants in the intervention arm opting to register for clinical trials. In a previous pilot study, we found that 45% of minority patients in the community adopted recommendations for medical treatments after exposure to tailored health messages, which compares to 25% who did without such exposure. Assuming a 20% increase in the likelihood of adopting health messages and a sample size of 100, the proposed study will have adequate power for a preliminary test of the hypothesis that exposure to health messages will foster greater uptake of tailored health messages and improvement in clinical trial health literacy level. Achieving the goal of a 20% increase would have an important public health impact regarding adoption of messages about clinical trials. A two-tailed test, with 80% power and $\alpha = 0.05$ comparing 25% to 45% requires 50 participants per arm. The study is powered to assess differences in participation rates between the two arms as well as the mediating effect of individual and contextual factors between tailored clinical trial messages and participation rates, considering a 23% attrition rate.

VI. DATA HANDLING

Confidentiality

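### The first analysis listed for Hypothesis 1 splits participants by literacy improvement at an unscheduled 2 months, and no comparison of the randomised arms on participation is clearly specified or named primary

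*Combined protocol and SAP*

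**What the plan says.** **What is to be tested.** Objective 1, Hypothesis 1 (stated near the front and again in Section IV) and the primary aim under Schedule of Events in Section III all set the tailored site against the standard one. The hypothesis concerns likelihood of participating in trials.

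**Section IV, analysis for Hypothesis 1.** After a sentence on primary and secondary goals and a remark on exposure in the intervention arm, the first analysis is: "To compare participants who exhibited improvement in health literacy and those who did not 2-months post-enrollment, t-tests and chi-squared tests will be used". Next comes a model for registration and referral: "Baseline subjective factors will be entered in a logistic regression model in order to determine which factors are associated with higher likelihood". Its first outcome is "registering to participate in clinical trials, contrasting individuals in the two study arms". Last: "Multivariate analysis of covariance will be used to assess effects of messages on the secondary outcome: health literacy scores".

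**Section V, under the Primary Objective label.** The first contrast, by Fisher's exact test and with no time point, is between "participants likely to show improvement in health literacy scores and those who are not". Registration follows: "This will also permit detection of a significant increase in the number of participants in the intervention arm opting to register for clinical trials". The sample size then comes from a two-sided comparison of arms, where "comparing 25% to 45% requires 50 participants per arm". The 25% and 45% are pilot rates at which patients "adopted recommendations for medical treatments after exposure to tailored health messages". The section closes by claiming power for arm differences in participation, allowing for 23% attrition.

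**Schedule.** Section III and Table 1 give baseline, 1 month and 3 months only. Section III asks willingness (a 1-5 item) at baseline and 1 month, and ResearchMatch registration at 1 month. Table 1 schedules Clinical Trials Literacy at all three visits.

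**The concern.** Improvers and non-improvers are not the randomised groups. Membership depends on what happens after allocation and on where a participant started, so a difference between them is not an effect of the website. The contrast also cannot be run at the stated time, because nothing is collected at 2 months.

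The plan's sections also disagree about what the main analysis is. Section V puts the literacy split first under the primary objective, Section IV calls literacy secondary, and the sample size rests on a comparison of arms. The one registration analysis in Section IV is framed as a search for associated baseline factors, with the arm contrast as a clause. An analyst could report the split, the registration model or another outcome as the test of Hypothesis 1 and cite the plan for each. At stake is whether the headline result is a randomised comparison at all.

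**Working it through.** **1. The texts side by side**

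| Element | Hypothesis 1 needs | Section IV, first analysis | Section IV, registration model | Section V, first contrast | Section V, sample size |
|---|---|---|---|---|---|
| Groups | Arms | Improved or not | Baseline factors, with an arm clause | Likely to improve or not | Arms |
| Outcome | Participation | Not stated | Registration, referral | Not stated | Adoption of messages |
| Test | One named test | t and chi-squared | Logistic regression | Fisher's exact | Two-sided, unnamed |
| Visit | A scheduled one | 2 months (none exists) | Not stated | Not stated | Not stated |
| Named primary | Yes | No | No | Under that label | Under that label, but no outcome, test and visit fixed |

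No column from the plan supplies arms, a participation outcome, a test and a scheduled visit together.

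**2. The plan's own figure**

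Inputs from Section V: p1 = 0.25, p2 = 0.45, two-sided 5%, 80% power, 23% attrition. Mean proportion 0.35.

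n per arm = [1.960 × √(2 × 0.35 × 0.65) + 0.842 × √(0.25 × 0.75 + 0.45 × 0.55)]² / 0.20² = [1.960 × 0.6745 + 0.842 × 0.6595]² / 0.04 = 88.1, so 89. The stated 50 does not reproduce.

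Power at n per arm = Φ[(0.20 × √n − 1.960 × 0.6745) / 0.6595].

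- n = 50: Φ[(1.414 − 1.322) / 0.6595] = Φ(0.140) = 55.6%.
- 77 completers (100 × 0.77, so 38.5 per arm): Φ[(1.241 − 1.322) / 0.6595] = Φ(−0.123) = 45.1%.
- Exact enumeration, chi-squared: 55.8% at 50 per arm; 46.1-47.5% at 38 and 39, depending on which arm is larger.
- Exact enumeration, Fisher's exact test: 47.7% and 38.6-40.9%.

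The shortfall is a separate problem. It enters here only because naming an arm test as primary means stating that test's power.

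**3. What the split would show if it were read as the test of Hypothesis 1 (illustration)**

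The documents give none of the following, so all are assumptions:

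- registration is the outcome compared between improvers and non-improvers;
- 77 completers, 38 and 39 by arm;
- standard normal literacy scores with baseline/follow-up correlation r, and any rise counted as improved;
- control registration 25%;
- chi-squared test at two-sided 5%, 20,000 simulated trials per cell.

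*Registration 45% v 25%, depending on arm only:*

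| Literacy shift in the tailored arm | Split rejects, r = 0.5 / 0.7 / 0.9 | Arm test rejects |
|---|---|---|
| None | about 5% throughout | 46-48% |
| 0.5 SD | 6% / 7% / 11% | 46-48% |

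*No website effect; registration a probit function of follow-up literacy:*

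| Probit slope per SD | Split rejects, r = 0.5 / 0.7 / 0.9 | Arm test rejects |
|---|---|---|
| 0.35 | 14% / 10% / 7% | about 5% |
| 0.66 | 30% / 19% / 10% | about 5% |
| 1.07 | 49% / 31% / 14% | about 5% |

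The split can nearly miss a real arm effect, and it can reject often when there is none. In the second table it detects a genuine association between literacy and registration. That becomes an error only when it is reported as a website effect.

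**The case against.** **The plan does mention arm contrasts.** A reader might infer that it contains no comparison of arms, or no test related to the one on which it was sized. The documents do not support that. Section III states a tailored-versus-control primary aim, Section IV puts an arm clause in the registration model, and Section V describes a two-sided comparison per arm and claims power for arm differences in participation. What stands is narrower: none is specified with outcome, test and visit, and none is named primary.

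**Listing order is not priority.** Section IV makes effectiveness the primary goal and factors favouring adoption the secondary goal, so the split may have been meant for the latter. That is a fair reading of Section IV. It does not explain Section V, which puts the same kind of split first under the primary objective.

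**The wording may mean improved or not, by arm.** Section V's hypothesis that exposure fosters literacy improvement gives this some support. Neither section says it, however, and it would still test an outcome that Section IV calls secondary.

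**Referral.** A reader might infer from Table 1 that referral is not an outcome. Study Design and Section III both list it. What they lack is an item and a visit.

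**This is a pilot.** Section V promises only a preliminary test. That bears on how much power is acceptable, not on whether the test compares the arms.

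**Conclusion.** The concern holds in this form. The first-listed analysis for Hypothesis 1 is not a comparison of arms and is set at a visit that does not exist. Section V gives the same kind of split first place under the primary objective, and no arm test of participation is clearly specified or named primary. This rests on the text alone.

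The size is illustrative and conditional on the assumptions listed, above all that registration is the outcome of the split. On that footing it rejects in about 5-11% of trials when a 45% v 25% arm difference is real and depends on arm only, and in about 7-49% when the website does nothing and registration follows literacy. The arm test gives about 46-48% and 5%.

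For an arm comparison of 25% v 45%, power is about 56% at 50 per arm and 45-48% with 77 completers by chi-squared, or about 48% and 39-41% by Fisher's exact test, the test that Section V names. Those rates describe adoption of treatment recommendations, so applying them to registration is an assumption.

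**What to change.** 1. **Name the primary test.** State in Section IV that Hypothesis 1 is tested by comparing the randomised arms, as allocated, on one participation outcome already collected at a scheduled visit. The sponsor chooses which. One option is ResearchMatch registration at 1 month, with a rule for participants already registered because they were recruited through ResearchMatch. Another is 1-month willingness adjusted for its baseline value.
2. **Relabel the split.** Replace 2 months with a scheduled visit, state the outcome compared, and label the improver and predictor analyses exploratory.
3. **Literacy.** Compare the Clinical Trials Literacy score by arm at 1 and 3 months, adjusted for baseline. Confirm that this is the health literacy score Section IV means, since Section III names a different instrument at baseline.
4. **Section V.** Put the chosen arm comparison under the primary objective and restate its power. If 25% v 45% is kept, use the figures above for the test chosen, and say that the rates are borrowed.
5. **Referral.** State the item and visit, and analyse it by arm at whichever visit it is collected.

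The cost is rewording Sections IV and V and a less favourable stated power. Registration and willingness at 1 month, and literacy at 1 and 3 months, need no new data. A larger sample is not part of this fix.

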Objective 1: To evaluate the comparative effectiveness of patient-centered messages to enhance clinical trial participation, through a culturally tailored website, accessed using iPads, versus NYU's standard clinical trial participation website.

Hypothesis 1: Participants exposed to tailored messages about clinical trial literacy will exhibit greater likelihood in participating in clinical trials than those exposed to NYU's standard website.

Objective 2: To determine whether psychosocial factors (awareness of clinical trial, intrinsic motivation, health literacy, and self-efficacy) and medical factors (risk behavior, history of preventive behavior, and clinical diagnoses) mediate greater likelihood of participating in clinical trials among individuals exposed to the intervention.

[figure not shown]
Hypothesis 2: Greater likelihood of participating in clinical trials will be mediated by greater health literacy and self-efficacy independent of other individual-level factors (medical, knowledge, attitude/beliefs, and intrinsic motivation) and contextual-level factors (social support and socio-economic position).

Study Design

Objective 1: To evaluate the comparative effectiveness of a culturally and linguistically tailored clinical trial literacy website in increasing likelihood of participating in clinical trials. To achieve this objective, we will use a randomized group design, assessing the following patient-centered outcomes: willingness to enroll in clinical trials and behavioral intent as well as likelihood of referring others to enroll in such trials) before and after exposure to a culturally-tailored clinical trial literacy website. Health literacy will be measured both before and post exposure to tailored messages.

Participants will be randomized into two groups. The intervention group (n=50) will have access to culturally tailored website. Participants in the control group (n=50) will have access to NYU 's standard trial participation website.

Study Flowchart

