Data acquisition for objective 1: We will use a randomized group design, assessing patient-centered outcomes (health literacy, willingness to participate in a clinical trial, willingness to refer others), contrasting participants who were exposed to health messages via NYU's standard clinical trial website (<http://www.med.nyu.edu/oct/home>) [control arm] and those exposed to the newly created culturally and linguistically tailored website [intervention arm]. They will all complete measures at baseline assessing demographics, general health status (Medical Outcomes Study Short Form), baseline health literacy measures (National Assessment of Adult Literacy), and willingness to participate in a clinical trial ("On a scale from 1 to 5, with 1 being 'not at all willing' and 5 being 'very willing', how willing would you be to participate in a clinical trial in the future?" Response anchors will be; not at all willing, somewhat unwilling, neutral, somewhat willing, and very willing).

At the 1-month debriefing, we will reassess participants' willingness to participate in a clinical trial, and ask whether or not they opted to register with ResearchMatch; an online volunteer clinical research registry. These data will help establish a model for future translational and dissemination research. At the end of the 2-year project, we expect to have developed a culturally-tailored clinical trial literacy website that could be widely accessed. There are over 31,000 racial/ethnic minority barbershops, beauty salons, and faith-based organizations across the United States that could use this non-traditional model promoting participation in clinical trials. The long-term goal is to use this infrastructure for dissemination of evidence-based clinical trial health literacy and participation at the community level.

Schedule of Events

The primary aim of this study is to compare the tailored materials to control information only materials that are not tailored to the population being studied. However, before the Intervention/Control study, all messages and online resources will be assessed using cognitive heuristic testing to ensure the website is user friendly and culturally and linguistically tailored to the population. Heuristic testing to ensure cultural and linguistic appropriateness of the resource will be conducted, followed by the Intervention/Control study.

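### The literacy MANCOVA does not name the baseline literacy score as a covariate, although that score is collected; this costs precision but does not bias the comparison.

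*Combined protocol and SAP*

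**What the plan says.** **Literacy.** Section IV (Hypothesis 1, Analysis) assigns a multivariate analysis of covariance to the secondary outcome. The covariate statement reads: "health literacy scores; effects of sociodemographic confounders will be adjusted". The baseline literacy score is not mentioned there. Study Design, Objective 1, states: "Health literacy will be measured both before and post exposure to tailored messages". Table 1 has a row for "Clinical Trials Literacy" marked at baseline, 1 month and 3 months.

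**Willingness (secondary note).** Study Design, Objective 1, lists among its outcomes "willingness to enroll in clinical trials and behavioral intent as well as likelihood of referring others". Section III (Data acquisition for objective 1) describes "assessing patient-centered outcomes (health literacy, willingness to participate in a clinical trial, willingness to refer others", and in the same sentence "contrasting participants who were exposed to health messages" through one website with those exposed through the other. That paragraph gives the wording of a 1–5 willingness item asked at baseline. The next paragraph adds: "At the 1-month debriefing, we will reassess" willingness. Section III also says, just before Table 1, that the table holds all outcome measures; it has no willingness row.

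**The concern.** A baseline measurement of the outcome is often the strongest available predictor of its follow-up value. Demographic variables may carry part of that information but seldom all of it. If the model is fitted with the named covariates and nothing else, the interval for the arm effect on literacy is wider than it needs to be. If the arms happen to differ in literacy at entry, part of that difference also carries through to the estimated effect. With about 100 participants, such an imbalance can be large relative to the effects of interest.

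For willingness, the matter is one of specification. An outcome to be contrasted between arms has no analysis assigned to it, so the choice stays open until the data are in.

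**Working it through.** **Plan's own figure.** There is none to reproduce. Section V gives no between-arm mean difference for literacy scores and no correlation between baseline and follow-up. What follows shows a range under stated assumptions, in units of the follow-up SD. It refers to the arm contrast at a single follow-up visit, not to the joint multivariate test.

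**Inputs**
- From the protocol: 50 per arm; 23% attrition (section V, no time point given). Retained: 100 × 0.77 / 2 = 38.5 per arm. Both sizes are shown.
- Assumed: correlation r = 0.3, 0.5, 0.7 between baseline and follow-up; sociodemographic factors explain a share R² = 0.20 of both scores and use 3 degrees of freedom.

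**Step 1: gain over the planned adjustment.** The correlation left after sociodemographic adjustment is p = (r − R²)/(1 − R²), and the further cut in residual variance is p².

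| r | p | further cut p² | residual variance 0.80 × (1 − p²) |
|---|---|---|---|
| 0.3 | 0.10/0.80 = 0.125 | 1.6% | 0.7875 |
| 0.5 | 0.30/0.80 = 0.375 | 14.1% | 0.6875 |
| 0.7 | 0.50/0.80 = 0.625 | 39.1% | 0.4875 |

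**Step 2: 95% half-width** = t × √(2/n) × √(residual variance).
- Planned model, 38.5 per arm: 1.993 × 0.228 × √0.80 = 0.406 SD.
- With baseline, 38.5 per arm: 0.403, 0.377 and 0.317 SD.
- At 50 per arm: 0.355 SD without baseline; 0.352, 0.329 and 0.277 SD with it.

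**Step 3: chance imbalance left in.** After sociodemographic adjustment, one standard error of baseline imbalance at 38.5 per arm is 0.228 × √0.80 = 0.204 SD. It moves the estimate by p times that amount: 0.03, 0.08 or 0.13 SD.

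**Step 4: sensitivity to the assumed overlap**
- R² = 0.10: cuts of 4.9%, 19.8% and 44.4%.
- R² = 0.20, with the sociodemographic information wholly contained in the baseline score: cut = 1 − (1 − r²)/(1 − R²), which is 6.25% at r = 0.5 and 36.25% at r = 0.7. This case cannot arise at r = 0.3, because r² = 0.09 is below 0.20.
- Baseline placed in the outcome vector, so that the arm-by-time contrast is a change score: moving it to the covariate side cuts variance by (1 − r)/2. That is 35%, 25% or 15%, reading r here as the correlation after any other adjustment.

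**Willingness: methods set beside outcomes.** In section IV:
- The t-tests and chi-squared tests compare literacy improvers with non-improvers.
- The logistic model takes "registering to participate in clinical trials, contrasting individuals in the two study arms", and referral, as outcomes.
- The MANCOVA takes literacy scores.
- The structural equation model, or the Bayesian network offered as its alternative, concerns the path to participation.

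Section V covers literacy improvement, registration, uptake of messages and mediation. None of these names the 1–5 score, and a binary logistic model would need a cut-point that is not given.

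**The case against.** The best case against the literacy point is that it concerns efficiency in a secondary outcome of a pilot. Randomization already makes the contrast unbiased, and at r = 0.3 the half-width hardly moves. All of that stands, and it limits the size of the point. It does not remove it, because the better analysis uses data already scheduled.

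A reader might infer that section IV restricts adjustment to sociodemographic factors. It does not say so: it names those factors and is silent on others. The authors may have meant baseline to enter, as a covariate or, through the word multivariate, as one of the outcomes. If so, one sentence settles it. In the outcome-vector reading baseline is already used, so imbalance is not ignored; the change score over-corrects it, and a covariate remains more precise.

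On willingness, registration may be the intended tested form of Hypothesis 1, with the 1–5 item left descriptive. The absence of a willingness row in Table 1 fits that reading. The listing of willingness among the arm-contrasted outcomes in section III does not.

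A reader might also infer that the willingness test runs at an inflated error rate. Null simulations with assumed category shares gave roughly 9–11% when the smallest p was taken from three common analyses, and roughly 12–13% from five. A repeat gave slightly wider ranges, and two analyses gave about 6–8%. These are upper illustrations. They require someone to run several tests of this review's choosing and report the smallest p, and nothing in the protocol says that will be done. The protocol also assigns no alpha to willingness.

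**Conclusion.** The point holds as a modest and nearly free improvement. The literacy MANCOVA, as written, does not name the baseline score. If baseline is in fact left out, the loss is negligible at a correlation of 0.3, noticeable at 0.5 and material at 0.7: a further 2%, 14% or 39% of residual variance under the 20% assumption. Neither the correlation nor the sociodemographic share is in the protocol, so no single figure can be defended and no power figure is given.

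Two stronger conclusions are not supported. The randomized comparison is not biased by the omission. The precision gain applies to the literacy scores; it does not carry over to the binary registration and referral outcomes or alter the sample-size argument in section V.

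The willingness gap is real as a matter of text, but it is secondary: an inconsistency between sections to be reconciled, not evidence of a compromised test.

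**What to change.** **Literacy.** In section IV, keep the MANCOVA and state that its outcomes are the 1-month and 3-month Clinical Trials Literacy scores. Add the baseline score of the same instrument as a covariate alongside the planned sociodemographic factors. The visits need naming because the improver comparison in section IV refers to 2 months, while the schedule has visits at 1 and 3 months.

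The cost is one sentence and one degree of freedom, with no new data. This holds for Clinical Trials Literacy. Section III names the National Assessment of Adult Literacy as the baseline health literacy measure, and Table 1 schedules no follow-up under that name. If that is the intended outcome, the instrument has to be reconciled first.

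**Willingness.** Reconcile section III, Table 1 and section IV. If willingness is to be tested between arms, add it to Table 1 at baseline and 1 month, and name one baseline-adjusted analysis before data are seen. One option is proportional-odds regression of the 1-month score on arm and baseline willingness. State its rank relative to registration, referral and literacy. If it is descriptive, say so. The cost is a sentence or two and, if it is tested, a stated position on multiplicity.

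### The Hypothesis 2 mediation analysis states no adjustment for baseline willingness, literacy or self-efficacy, although all three are collected, so pre-existing differences could be read as mediation

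*Combined protocol and SAP*

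**What the plan says.** Hypothesis 2 appears in Section 1 and, almost unchanged, in Section IV. The Section IV form reads: "Greater likelihood of participating in clinical trials will be mediated by greater health literacy and/or self-efficacy", and continues "independent of other individual-level factors (medical, knowledge, attitude/beliefs, and intrinsic motivation) and contextual-level factors (social support and socio-economic position". No time point is attached to any of these factors.

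The analysis paragraph under it says that "SEM will determine influences of mediating/moderating factors on the role of tailored messages in improving participation rates in existing clinical trials", and then "Specifically, we will use moderated path analysis from Baron and Kenny's model". It writes no equations, lists no covariates and does not discuss confounding between mediator and outcome. Entering baseline factors is mentioned only for the Hypothesis 1 logistic model.

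The baseline scores will exist. Section III (data acquisition for objective 1) collects "baseline health literacy measures (National Assessment of Adult Literacy), and willingness to participate in a clinical trial" at baseline, and at 1 month "we will reassess participants' willingness to participate in a clinical trial". Table 1 schedules Clinical Trials Literacy and the "Internet Self-efficacy Scale" at baseline, 1 month and 3 months. The willingness item is described in Section III but is not a row of Table 1.

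**The concern.** Randomisation makes the arms comparable, so the effect of arm on follow-up literacy or self-efficacy is unconfounded. It does nothing for the relation between follow-up literacy and follow-up willingness within an arm. People who start more literate tend to finish more literate, and people who start more willing tend to finish more willing. If the two starting values are correlated, the two follow-up values are correlated even when literacy has no effect on willingness. A path model without the baseline scores attributes that correlation to the mediator.

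The protocol's own rationale makes a positive baseline correlation plausible: its background section links low health literacy with low trial participation. At stake is a claim about mechanism. The trial could report that the website works through literacy when it does not.

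**Working it through.** The plan claims power for mediation in Section V but gives no path coefficient or correlation, so it has no mediation figure to reproduce. The check asks how often mediation is declared when the mediator has no effect.

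**Inputs from the documents.** 100 participants and 23% attrition (Section V) give 100 × 0.77 = 77 completers, taken as 38 and 39 per arm. Two-sided alpha is 0.05 (Section V).

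**Assumed inputs, because the documents give none.** Arm effect on the mediator a = 0.5 SD. Baseline-to-follow-up correlation r = 0.6 for both scores. Correlation of baseline literacy L0 with baseline willingness W0: ρ = 0.3, 0.5 or 0.7. No other covariates.

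**Model.** With T the arm, mediator M = aT + r·L0 + error and outcome Y = r·W0 + error. M and Y have unit variance within arm, and the true mediator effect b is 0. Mediation is declared when the arm-to-mediator and mediator-to-outcome paths are both significant.

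**Step 1: bias.** Without baseline terms, the estimated mediator path tends to Cov(M,Y | T) / Var(M | T) = r²ρ, and the indirect effect to a·r²ρ.

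**Step 2: chance that the mediator path is significant.** SE ≈ √[(1 − b²)/(77 − 3)], with critical value 1.993.

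**Step 3: arm-to-mediator path.** SE = √(1/38 + 1/39) = 0.228, and 0.5/0.228 = 2.19, so power is about 58%. With baseline literacy in the equation the residual SD is √(1 − 0.36) = 0.8, the ratio is 2.19/0.8 = 2.74, and power is about 77%.

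**Step 4: both significant, without baseline terms (normal approximation).**

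| ρ | r²ρ | a·r²ρ | SE | ratio | mediator path significant | × 0.58 |
|---|---|---|---|---|---|---|
| 0.3 | 0.108 | 0.054 | 0.116 | 0.93 | 15% | 9% |
| 0.5 | 0.180 | 0.090 | 0.114 | 1.57 | 34% | 20% |
| 0.7 | 0.252 | 0.126 | 0.112 | 2.24 | 60% | 35% |

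With the baseline terms the mediator path is significant about 5% of the time, so the joint rate is about 0.77 × 0.05 = 3.9%.

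**Step 5: simulation of the same model.** False mediation is about 10%, 21% and 35% without baseline terms and 3-4% with them. Power for the arm-to-mediator path rises from about 59% to 77%.

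**Step 6: sensitivity, without baseline scores.**
- Binary participation outcome: about 7%, 13% and 21%.
- Continuous outcome, adjusting for one proxy of baseline literacy and one of baseline willingness, each correlated 0.6 with its target: about 6%, 7% and 11%.
- r = 0.4: bias is 0.16ρ = 0.048, 0.080 and 0.112. The Step 2 formula gives 6.5%, 10% and 15.5%, and multiplying by 0.58 gives about 4%, 6% and 9%.
- n = 100, r = 0.6: 12% and 30% at ρ = 0.3 and 0.5, so more participants make it worse.
- ρ = 0, or no arm effect on the mediator: near or below 5%, and at most 2%, respectively.

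**The case against.** The strongest reply is that the plan is silent rather than wrong. The list of factors is the wording of a hypothesis, not a covariate list, and no model is written out. A reader might infer that the plan rules out baseline adjustment. The documents do not support that: they neither include nor exclude it. This part of the objection stands, and the point is therefore that no adjustment is stated.

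Second, knowledge, attitudes and intrinsic motivation are named and could stand in for starting literacy and willingness. If they are good baseline proxies, much of the excess goes. But they are undated, and Table 1 lists no instrument for attitudes, motivation or social support. Objective 2 also treats intrinsic motivation as a possible mediator, so a post-exposure value might be used. Proxies reduce the problem; the collected baseline scores remove the part due to those scores.

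Third, the analysis paragraph speaks of participation rates, which suggests a binary outcome, and there the inflation is smaller. That stands, and both sets of figures are given. Likewise, if a significant total arm effect is required as a first step, as in the classical causal-steps procedure, the tabulated rates are ceilings.

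Fourth, a reader might infer that false mediation will occur, or that the arm comparison in Hypothesis 1 is compromised. Neither follows. The first needs a website effect on the mediator and a baseline correlation that the documents do not quantify. The second is untouched, because that comparison is randomised.

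**Conclusion.** The concern holds as an omission from the stated Hypothesis 2 analysis. With no baseline adjustment stated, pre-existing differences in literacy and willingness could be reported as mediation. Under the main assumptions the false-mediation rate is about 10% to 35% for continuous willingness and about 7% to 21% for binary participation, against 3-4% with the baseline terms.

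These figures describe a model with no other covariates and rest on assumed correlations. The 35% belongs to the highest baseline correlation tried. With baseline-to-follow-up correlation 0.4 the rates are close to nominal at baseline correlations 0.3 and 0.5, and about 9% at 0.7. The direction does not depend on the exact values, provided that both correlations are positive and the website moves the mediator. The point is worth acting on because the scores are already collected and, under the same assumptions, using them also raises power for the arm-to-mediator path.

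**What to change.** Add to the Hypothesis 2 analysis in Section IV:

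- The mediator equation includes the baseline score of the same instrument that serves as mediator: Clinical Trials Literacy or the Internet Self-efficacy Scale from Table 1. Naming the instrument matters because Section III also mentions the National Assessment of Adult Literacy, as a baseline measure.
- The outcome equation includes that baseline mediator score and the baseline 1-to-5 willingness item. This applies also when the outcome is registration, which has no baseline score of its own.
- The other factors named in the hypothesis enter only as baseline values.
- The mediation result is reported as exploratory.

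Table 1 should also list the willingness item at baseline and 1 month, to match Section III.

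The cost is a short SAP addition and a few degrees of freedom, with no new data for the three baseline scores. Unmeasured mediator-outcome confounding remains, which is why the result should stay exploratory.
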